#### **6.3.2. Secondary Endpoints**

The secondary endpoints of the study are:

- The incidence and the severity of AEs and SAEs in STP206-treated subjects compared to control subjects from baseline through six months after the last dose of blinded study treatment
- The incidence of clinical events (NEC, sepsis/bacteremia, feeding intolerance, death, morbidity/complications of prematurity) in STP206-treated subjects compared to control subjects from baseline through hospital discharge
- The assessment of the fecal shedding of STP206 organisms in STP206-treated subjects compared to its baseline and to control subjects through the last dose of blinded study treatment

- The assessment of the changes in routine clinical parameters in STP206-treated subjects compared to control subjects at baseline through the last dose of blinded study treatment
- The assessment of the progression of standard neonatal growth parameters in STP206-treated subjects compared to control subjects through the 6-month postdosing visit.

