**Figure 1: Treatment Group Sequence**

All neonates enrolled will receive daily doses of blinded study treatment through 34 weeks of post-conceptual age or neonatal intensive care unit (NICU) discharge, whichever comes first. While in the NICU, neonates will be evaluated daily for signs/symptoms of NEC, feeding volumes/feeding tolerance, AEs, and concomitant medications. Physical examinations and vital signs will be performed daily during the dosing period and at the end of dosing/NICU discharge. Growth assessments will be performed every other week while in the NICU and at the end of dosing/NICU discharge. Assessments for complications of prematurity, including retinopathy of prematurity (ROP), intraventricular hemorrhage (IVH), and bronchopulmonary dysplasia (BPD) will be

performed at protocol defined timeframes (see [Section 11.2](#)). Neonates enrolled in the study will have fecal/meconium samples collected daily through 4 days following the start of dosing and weekly thereafter until NICU discharge to determine fecal shedding of [REDACTED] (STP6) and [REDACTED] (STP11).

Following completion of blinded study treatment dosing, neonates will be evaluated at 1 week, 1 month, 3 months, and 6 months for safety and growth assessments.

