#### *13.2.3.4. Fecal Shedding Data Analysis*

Fecal shedding [REDACTED] for each treatment group will be assessed by quantitative and/or qualitative methods. Counts will be summarized as a continuous measure and will be summarized descriptively by treatment at each time point. Qualitative responses will be categorized and analyzed by counts and percentages and summarized by treatment at each time point.

In addition, change from baseline will be calculated and summarized descriptively by treatment to determine whether fecal shedding values return to baseline levels.

Duration of fecal shedding will be summarized descriptively by treatment group.

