5.2 Changes from the Analyses Planned in the Protocol

The definition of the Intent-to-treat analysis population was changed in this SAP to include all subjects that are randomized regardless of dosing status.

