6.2 Time Point Algorithms

6.2.1 Relative Day

The date of first dose of study treatment will be considered as study day 1, and the day before the first dose of study treatment will be relative day -1. Study days will be calculated as follows only when the full assessment date is known (i.e., partial dates will have missing study days).

For days on or after the first dose of study treatment:

Date of Assessment – Date of First Dose of study treatment + 1.

For days before the first dose of study treatment:

Date of Assessment – Date of First Dose of study treatment.

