6.2.2 Windows

The time schedule described in the protocol for each scheduled activity will be followed as closely as possible. The time windows noted in Table 4 will be used for analysis purposes.

Table 4: Analysis Visit Windows for Dosing Period and Post Dosing

Nominal Visit during dosing period (Target Day)	Protocol Window	Study Day Analysis Visit Window Range
Baseline	Collected at birth, screening, or/and Week 1 Day 1 before study dosing	Sample assessment date < Date of First Dose of study treatment
1 Hour ^a	1 Hour + 10 minutes	1 Hour + 30 minutes

Nominal Visit during dosing period (Target Day)	Protocol Window	Study Day Analysis Visit Window Range
2 Hour ^a	2 Hour \pm 10 minutes	2 Hour \pm 30 minutes
3 Hour ^a	3 Hour \pm 10 minutes	3 Hour \pm 30 minutes
4 Hour ^a	4 Hour \pm 10 minutes	4 Hour \pm 30 minutes
8 Hour ^a	8 Hour \pm 10 minutes	8 Hour \pm 30 minutes
12 Hour ^a	12 Hour \pm 10 minutes	12 Hour \pm 30 minutes
16 Hour ^a	16 Hour \pm 10 minutes	16 Hour \pm 30 minutes
20 Hour ^a	20 Hour \pm 10 minutes	20 Hour \pm 30 minutes
24 Hour ^a	24 Hour \pm 10 minutes	24 Hour \pm 30 minutes
Week 1 (Day 1-4) ^b	day 1, day 2, day 3, day 4	day 1, day 2, day 3, day 4
Week 1 (Day 5-7) ^{b,c,d}	day 5, day 6, day 7	day 5, day 6, day 7
Week 2 (Day 14) ^{b,d}	13 to 16 days	13 to 17 days
Week 3 (Day 21) ^b	20 to 22 days	18 to 24 days
Week 4 (Day 28) ^{b,d}	25 to 32 days	25 to 32 days
Week 5 (Day 35) ^b	34 to 36 days	33 to 38 days
Week 6 (Day 42) ^{b,d}	41 to 42 days	39 to 45 days
Week 7 (Day 49) ^b	48 to 50 days	46 to 52 days
Week 8 (Day 56) ^{b,d}	55 to 57 days	53 to 59 days
Week 9 (Day 63) ^b	62 to 64 days	60 to 66 days
Week 10 (Day 70) ^{b,d}	69 to 71 days	67 to 73 days
Week 11 (Day 77) ^b	76 to 78 days	74 to 80 days
End of Dosing or Hospital Discharge ^{b,d} (for Growth Assessment, and fecal sample only)	Not specified	For fecal sample: sample assessment date - last dose date \geq 0 For growth assessment: 0 \leq sample assessment date - last dose date \leq 5 days
Nominal Visit during Post Dosing		Post Study Day Analysis Visit Window Range^e
Post Dosing 1 Week ^d	5 to 9 days	6day \leq (assessment date – expected last dose date+1) \leq 13 days
Post Dosing 1 Month ^d	30 to 35 days	21 days \leq (assessment date – expected last dose date+1) \leq 35 days
Post Dosing 3 Month ^d	85 to 99 days	85 \leq (assessment date – expected last dose date+1) \leq 99 days

Nominal Visit during dosing period (Target Day)	Protocol Window	Study Day Analysis Visit Window Range

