Post Dosing 6 Month ^d	181 to 195 days	181 <= (assessment date – expected last dose date+1) <= 195 days
Post Dosing 18 Month/End ^d	Not specified	520 <= (assessment date – expected last dose date+1) <= 576 days
Withdrawal Prior to Post Dosing 6 Month ^d	Not specified	assessment date >= date of withdrawal and (assessment date – expected last dose date+1) <= 181 days
Withdrawal between Post Dosing 6 and 18 Month ^d	Not specified	assessment date >= date of withdrawal and 196 days < (assessment date – expected last dose date+1) < 520 days

- a- Windows for vital sign measurements and physical examinations.
- b- Window for fecal sample.
- c- Window for IVH measurement.
- d- Windows for growth assessment (note that Post Dosing 18 Month data will only be presented in listings).
- e- Windows for Post Dosing may be adjusted to account for patients that terminated dosing early. For example, if a subject early terminates dosing at Week 10 but was expected to complete dosing at Week 11, then the Post Dosing window will be adjusted to reflect planned time point after expected dosing completion.

If a subject has more than 1 assessment occurring in the same visit window, the data from the visit closest to the scheduled study day will be used for summaries. If two assessments have the same distance from the scheduled study day, the assessment after the scheduled study day will be used for the analyses.

If multiple assessments occur as Baseline (screening or Day 1 prior to dosing), then the last assessment before the first study dose will be used for the analyses.

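### SAP Table 4 places weekly stool samples by days since first dose with no cut at last dose, contrary to the stated shedding endpoint, and the SAP omits two protocol-planned shedding analyses without listing the change

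*SAP*

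**What the plan says.** **Endpoint.** Protocol 6.3.2 defines the shedding endpoint as STP206 organisms in treated infants "compared to its baseline and to control subjects through the last dose of blinded study treatment". SAP 6.6 repeats the through-last-dose limit for the presence count.

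**Collection.** Protocol 7.1 has stool sampled daily through 4 days and "weekly thereafter until NICU discharge to determine fecal shedding". Protocol 10.4 also plans post-dosing samples until discharge.

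**Windows.** SAP 6.2.1 defines study day as "Date of Assessment – Date of First Dose of study treatment + 1". In SAP 6.2.2, Table 4, the Week 2 to Week 11 rows that carry the stool footnote are ranges of study days with no reference to last dose. The one stool row tied to last dose is End of Dosing or Hospital Discharge: "For fecal sample: sample assessment date - last dose date" must be zero or more. The growth entry in the same cell is capped at 5 days. Footnote e says "Windows for Post Dosing may be adjusted to account for patients that terminated dosing early", but no Post Dosing row carries the stool footnote.

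**Analyses.** Protocol 13.2.3.4 plans two summaries beyond counts by time point: "change from baseline will be calculated and summarized descriptively by treatment to determine whether fecal shedding values return to baseline levels", and "Duration of fecal shedding will be summarized descriptively by treatment group". SAP 8.7.4 gives presence and quantity by time point and applies change from baseline to vital signs only. SAP 6.4.2 adds time to first detection. Fecal shedding duration appears nowhere in the SAP. The only entry in SAP 5.2 is that "The definition of the Intent-to-treat analysis population was changed in this SAP". Protocol 13.2.5 requires departures from the protocol-defined analysis to be documented in the SAP.

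**The concern.** A programmer who follows Table 4 literally will not produce the endpoint as defined. A weekly row would combine infants on treatment with infants who have finished or stopped, and which infants are off drug depends on gestational age. Week-by-week profiles and comparisons between birth weight strata would then mix shedding under dosing with shedding after dosing.

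The unbounded End of Dosing row can hold samples taken at very different times off drug. It also overlaps the weekly rows, and no rule says which row a sample belongs to.

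The second gap is independent of the first. STP206 is a live product, and shedding of each component is a secondary objective. The protocol says it will examine whether shedding returns to baseline. The SAP plans no within-infant change and no duration of shedding, and does not record that these were dropped.

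**Working it through.** **1. Dosing length.** Input: the ten gestational-age rows in SAP 6.2.3 (the same as Protocol Table 2). Formula: intended days = 7 × (34 − completed weeks). For 23 weeks, 7 × 11 = 77; for 32 weeks, 7 × 2 = 14. All ten stated values are reproduced: 77, 70, 63, 56, 49, 42, 35, 28, 21, 14.

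**2. Windows against intended last dose.** First dose is day 1 and no days are missed, so the last dose day equals the intended days. A window is wholly off drug if it starts after that day. It straddles if it starts on or before that day and ends after it.

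| Week | Study days | Rows wholly off drug | Straddling row (days off drug) | Rows wholly on drug |
|---|---|---|---|---|
| 2 | 13–17 | 0 | 32 wk (3 of 5) | 9 |
| 3 | 18–24 | 1 | 31 wk (3 of 7) | 8 |
| 4 | 25–32 | 2 | 30 wk (4 of 8) | 7 |
| 5 | 33–38 | 3 | 29 wk (3 of 6) | 6 |
| 6 | 39–45 | 4 | 28 wk (3 of 7) | 5 |
| 7 | 46–52 | 5 | 27 wk (3 of 7) | 4 |
| 8 | 53–59 | 6 | 26 wk (3 of 7) | 3 |
| 9 | 60–66 | 7 | 25 wk (3 of 7) | 2 |
| 10 | 67–73 | 8 | 24 wk (3 of 7) | 1 |
| 11 | 74–80 | 9 | 23 wk (3 of 7) | 0 |

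Totals over 10 rows × 10 weeks = 100 pairings: 45 wholly off, 10 straddling, 45 wholly on.

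**3. Early stoppers.** A 23-week infant whose dosing ends at the 54-day minimum (doses taken as consecutive) has the Week 9 to Week 11 windows, days 60–80, wholly off drug.

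**4. Overlap with End of Dosing.** Any sample on or after last dose satisfies the End of Dosing condition. Up to day 80 it also falls in a weekly window, except on days 8–12, which no window covers. The overlap is routine: the intended last dose days (14, 21, …, 77) are exactly the target days of Weeks 2 to 11. The closest-assessment rule in SAP 6.2.2 chooses between samples inside one window; it does not choose between windows.

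**5. Effect on a weekly percentage (illustration only).** With a share f of off-drug samples, observed = (1 − f) × p_on + f × p_off. None of the three inputs is known for neonates.

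- Assuming p_on = 90%, p_off = 10–30% and f = 25–50%: lowest 0.5 × 90 + 0.5 × 10 = 50%; highest 0.75 × 90 + 0.25 × 30 = 75%.
- Taking p_on from the adult study in Protocol 5.3.2.1 (STP6 detected in 4 of 17 treated subjects, 24%) with p_off = 10%: 0.75 × 24 + 0.25 × 10 = 20.5%, and 0.5 × 24 + 0.5 × 10 = 17%.
- If p_off = p_on there is no shift; if p_off is higher, the shift is upward.

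**6. Omitted analyses.** Setting Protocol 13.2.3.4 beside SAP 8.7.4 and 6.4.2: presence and quantity by time point are carried over. Change from baseline and duration are not. Time to first detection measures onset, not duration. The titles of Tables 14.3.6.4.1 to 14.3.6.4.3 name neither.

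**The case against.** **The SAP does state the limit.** SAP 6.6 confines presence to the period through last dose, Table 4 heads these rows as visits during the dosing period, and SAP 8.7.4 ends its stool time points at end of dosing or discharge, whichever is first. This stands. It is therefore wrong to infer that the SAP ignores last dose: the fault is a contradiction between the stated scope and the window definitions that would be programmed.

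**Off-drug samples may be few.** Protocol 7.2.1 expects discharge at 34 weeks, where dosing ends, and the post-dosing schedule has no stool row. This also stands as to number. A reader might take 45 of 100 to mean that nearly half the samples are off drug, but the count weights every row and window equally and says nothing about how many infants remain in hospital. Some longer stays are foreseen: Appendix B assesses BPD at 36 weeks or discharge, and Protocol 9.5.2 keeps most treated infants who are withdrawn in follow-up.

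**A late sample need not displace an earlier one.** The closest-assessment rule, and the last-day stool sample that Protocol 11.3.2.8 requires when dosing stops before 34 weeks, would usually favor a sample near last dose. This largely stands. But the End of Dosing row gives no scheduled study day, and a late sample is still eligible when no nearer one exists.

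**Little is lost on persistence.** The endpoint runs only through last dose, pre-dose values are tabulated, Listing 16.2.8.5.1 covers stool samples, baseline stool is collected only if available, and table shells are in a separate document. These points limit the consequence. They do not remove the comparison with baseline, which is in the endpoint itself, or the duty to record the change.

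**Conclusion.** The point holds as a conflict in the text plus an undisclosed omission. Table 4 as written does not deliver the through-last-dose endpoint, its End of Dosing stool row is unbounded and overlaps the weekly rows, and two protocol-planned summaries are missing from the SAP without an entry in 5.2.

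The size of any distortion is unknown. It depends on how many infants stay in the NICU after last dose and on detection on and off drug, none of which the documents give. A reader might infer that on-treatment shedding is understated by some definite amount. That does not follow, because it requires lower detection off drug, and Protocol 5.4 itself contemplates colonization of the bowel. The percentages in the working are illustrative only.

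All comparisons are exploratory and descriptive, and the stopping criteria in Protocol 7.1.1 do not use stool results, so no error rate, sample size or stopping decision is affected. The finding on omitted analyses needs no assumption about sample numbers, but rests on the SAP text and table titles because the shells were not available. The changes should be made before database lock; they do not call the design into question.

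**What to change.** 1. In SAP Table 4, flag each stool sample as on or off drug by the actual last dose date, and limit weekly summaries to samples on or before last dose.
2. Bound the End of Dosing stool window, for example at 0 to 5 days after last dose to match growth. Restricting it to the last-dose day alone would discard usable samples when no stool is produced that day. State which row takes a sample that fits both, including one dated on the last dose day.
3. Tabulate later samples by days since last dose.
4. Restore to SAP 8.7.4 the change from baseline (where a baseline stool exists) and the duration of shedding, with a definition of duration; or list and justify their removal in SAP 5.2.

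The cost is SAP text and a few descriptive tables, using dose and sample dates already recorded. The drawback is smaller counts at later weeks: under intended dosing, the gestational-age rows still contributing on-drug samples fall from 10 at Week 2 to 9 at Week 3, and by one each week to 1 at Week 11 (23-week infants only).

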### 7.1.2. Study Periods

Subject participation will be classified into four study periods:

- Screening Period – from the time of informed consent through administration of the first dose of study drug.
- Treatment Period – this will be the period when subjects are actively being administered blinded study treatment.
- Immediate Follow-up Period – this period will begin the day following the last dose of blinded study treatment through 30 days following administration of the last dose.
- Long-Term Follow-up Period – this period will begin after completion of the immediate follow-up period.

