### 9.5.2. Withdrawal Procedures

All subjects who are withdrawn from the study will have a post dosing assessment completed. All subjects who received blinded study treatment, with the exception of those for whom consent is withdrawn, will be followed for all subsequent study assessments per study protocol.

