#### *11.3.3.4. 6 Months/End of Study*

The following procedures will be performed between 181 and 195 days following completion of dosing:

- Physical Examination
- Vital Signs
- Growth Assessment
- Assessment of AEs
- Assessment of concomitant medication changes

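### SAP Table 4 assigns post-dosing growth visits from an undefined expected last dose date plus 1, so some on-time visits miss their window; separately, the four growth classes cover 4 of 9 weight-by-head combinations (minor)

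*SAP*

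**What the plan says.** Protocol 11.3.3 schedules the post-dosing visits at one week ± 2 days, 30 to 35 days, 85 to 99 days and, for the last, "between 181 and 195 days following completion of dosing". Protocol 7.1.2 uses the same clock for the immediate follow-up period: "this period will begin the day following the last dose of blinded study treatment".

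SAP 6.2.2, Table 4, repeats these ranges as the protocol window but assigns visits by another formula. For 6 months it is "181 <= (assessment date – expected last dose date+1) <= 195 days". The other post-dosing rows have the same form, with limits 6 to 13 (1 week), 21 to 35 (1 month) and 85 to 99 (3 months). Footnote e allows adjustment for infants who stop early. Its example is a stop at Week 10 when Week 11 was expected: "then the Post Dosing window will be adjusted to reflect planned time point after expected dosing completion".

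The End of Dosing row in the same table uses "sample assessment date - last dose date", with no +1 and no expected date, and accepts 0 to 5 days for growth. The early-withdrawal row accepts "assessment date >= date of withdrawal and (assessment date – expected last dose date+1) <= 181 days". The tie rule begins "If a subject has more than 1 assessment occurring in the same visit window" and does not deal with one assessment that fits two windows.

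SAP 6.4.2 defines four growth classes from weight and head circumference percentiles: AGA, SGA/Head-Spared, SGA/Symmetric and LGA. SAP 8.7.4 displays those four.

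**The concern.** Growth progression through the 6-month post-dosing visit is a secondary endpoint (protocol 6.3.2), and Table 4 decides which measurements enter each row of the growth tables. Three features look wrong.

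- The anchor date is not defined. SAP 6.2.3 gives intended dosing days and SAP 4.1 gives 34 weeks or hospital discharge; neither is named as the expected date. Two programmers could produce different tables from the same data.
- The +1 changes the scale, but only some of the limits were changed to match.
- Some assessments fit two rows. Infants withdrawn under protocol 9.5.1 are still in follow-up, since treated infants whose consent is not withdrawn "will be followed for all subsequent study assessments per study protocol". Their scheduled visits can meet both the early-withdrawal row and a scheduled row.

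The classes are a separate gap: an infant whose weight and head percentiles match none of the four definitions appears nowhere in the percentages.

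**Working it through.** **Inputs.** Permitted days d after the last dose (protocol 11.3.3): 5–9, 30–35, 85–99 and 181–195, that is 5 + 6 + 15 + 15 = 41 days. Taking 7 ± 2 as 5–9, these reproduce the protocol-window column of Table 4. SAP limits on the computed value x: 6–13, 21–35, 85–99 and 181–195.

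**Formula.** Let k be the number of days by which the actual last dose precedes the expected date. For a visit d days after the actual last dose, x = d − k + 1.

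**Dosing ends as expected (k = 0), so x = d + 1.**
- 1 week: 5–9 becomes 6–10, inside 6–13. The lower limit was moved from 5 to 6.
- 1 month: day 35 becomes 36, above 35.
- 3 months: day 99 becomes 100, above 99.
- 6 months: day 195 becomes 196, above 195.

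Three of 41 permitted days miss their window and fall in no other post-dosing window. Attaching the +1 to the dose date instead (x = d − 1) loses days 5, 6, 85 and 181. Dropping it altogether loses day 5 from the 1-week row, whose lower limit is 6.

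**Dosing ends early, visits timed from the actual last dose.** Permitted days outside their own window:

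| k | 1 week | 1 month | 3 months | 6 months | All |
|---|---|---|---|---|---|
| 0 | 0/5 | 1/6 | 1/15 | 1/15 | 3/41 |
| 1 | 1/5 | 0/6 | 0/15 | 0/15 | 1/41 |
| 7 | 5/5 | 0/6 | 6/15 | 6/15 | 17/41 |
| 13 | 5/5 | 3/6 | 12/15 | 12/15 | 32/41 |
| 16 or more | 5/5 | 6/6 | 15/15 | 15/15 | 41/41 |

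Footnote e's example gives k = 77 − 70 = 7 if the last dose is on day 70, and k = 77 − 64 = 13 if it is on day 64.

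**Spread between two candidate anchors.** Take an infant born at 23 weeks 6 days (167 days) with the first dose 4 days after birth. The intended 77 days end on day 4 + 77 − 1 = 80 after birth. The age of 34 weeks 0 days is reached on day 238 − 167 = 71. The two dates differ by 9 days with no early stopping.

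**Two rows.** At k = 0, an assessment on day 5 meets End of Dosing (5 ≤ 5) and 1 Week (x = 6). The early-withdrawal row takes every assessment from withdrawal up to x = 181, so it overlaps the 1-week, 1-month and 3-month rows and the first day of the 6-month row.

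**Growth classes.** Three weight bands by three head bands make 9 combinations, of which 4 have a class. The five without are weight <10th with head >90th; weight 10th–90th with head <10th; weight 10th–90th with head >90th; weight >90th with head <10th; and weight >90th with head 10th–90th. Example from protocol Appendix D: a boy at 34 weeks weighing 2000 g (range 1810–2763) with a 29.0 cm head (range 29.5–33.6) has no class.

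**The case against.** The strongest reply is that the expected-date anchor is deliberate. Study-week rows up to the planned end of dosing, followed by post-dosing rows counted from it, compare infants at similar ages. That is a coherent design and may be what was meant. It still needs a defined date and windows wide enough to hold visits timed on the protocol's clock; the 3- and 6-month windows are no wider than the protocol's.

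The early-stop counts are also conditional. If sites timed visits from the expected date, only the edge-day misses would remain. If the expected date takes account of hospital discharge, k is 0 for discharged infants.

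Several stronger readings are tempting but not supported:

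- *Post-dosing visits also fall in study-week windows.* The day numbers can coincide, but Table 4 has separate blocks for the dosing period and for post-dosing, which may exclude this.
- *The earlier dosing stops, the more days are lost.* Not throughout: 3 of 41 at k = 0 but 1 of 41 at k = 1, and the 1-month row loses none for k = 1 to 10.
- *Day 5 is counted twice in the tables.* Only if End of Dosing growth is displayed, and SAP 8.7.4 does not list it.
- *Growth visits ran on a different six-month clock.* The note in SAP 8.7.2 concerns adverse-event follow-up, and the corrected-age text in SAP 6.6 is garbled. Neither shows it.
- *A stated share of infants is unclassified.* That would need a weight-head correlation the documents do not give, and small-for-gestational-age infants are excluded at entry.
- *Continuous growth summaries are absent.* SAP 7.1 gives a format for continuous measures, the shells are in a separate document and tables may be added, so absence is not shown.

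**Conclusion.** The point holds and is minor. Without any assumption about early stopping, Table 4 leaves out three permitted visit days (35, 99 and 195) when dosing ends as expected, rests on an undefined date, and has no rule for an assessment that fits two rows. The four growth classes omit five of nine combinations, so the class percentages need not account for every measured infant.

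The larger losses (17 of 41 permitted days at k = 7, all from k = 16) require visits timed from the actual last dose and an expected date later than it. The documents do not show how many visits are affected, and no direction of bias can be stated. The effect is confined to descriptive growth tables. SAP 7.1 makes every comparison exploratory, no test depends on these rows, and all growth values stay in the listings.

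**What to change.** (a) Define the anchor date and make each window contain every permitted day on that anchor. One option is assessment date minus actual last dose date, with windows 5–12, 20–35, 84–99 and 180–195. These hold all 41 permitted days and every day accepted now at k = 0. If age alignment is intended, keep the expected date but define it, widen the windows accordingly, and show the other version as a sensitivity table.

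(b) Add a precedence rule for an assessment that fits two rows: a scheduled post-dosing visit goes to its post-dosing row, and day 5 goes to 1 Week. Do not cut the study-week growth windows at the last dose. Protocol 7.1 has growth measured every other week in the NICU, and early stoppers remain in follow-up, so those in-NICU measurements should stay in their study-week rows. Reserve the early-withdrawal row for the visit in protocol 11.4.

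(c) Report weight and head circumference categories separately or as a full 3 × 3 table, or add an unclassified row, so that every measured infant is counted.

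The cost is SAP wording and a little more programming on data already collected. The downside of the actual-date anchor is that infants who stop early are k days younger at each nominal visit than those who finish as expected.
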